3.2 Exclusion Criteria

- Patients with peripheral neuropathy > CTCAE grade 2
- Patients receiving concurrent corticosteroids at the time protocol therapy is initiated other than for physiologic maintenance treatment.
- History of allergic reaction (including erythema nodosum) to lenalidomide
- Concurrent use of complementary or alternative medicines that would confound the interpretation of toxicities and antitumor activity of the study drugs.
- Patients with contraindication to thromboprophylaxis.
- Unacceptable cardiac risk factors defined by any of the following criteria: Patients with congenital long QT syndrome, any history of ventricular fibrillation or torsade de pointes, bradycardia defined as HR< 50 bpm, Left ventricular ejection fraction < 30%
- Patients who have received targeted or investigational agents within 2 weeks or within 5 half-lives of the agent and active metabolites (whichever is longer) and who have not recovered from side effects of those therapies.
- Patients who have undergone major surgery ≤ 2 weeks prior to starting study drug or who have not recovered from the side-effects of surgery.
- Patients with known positivity for human immunodeficiency virus (HIV), or hepatitis C. Baseline testing for HIV and hepatitis C is not required
- Patients with a history of another primary malignancy that is currently clinically significant or currently requires active intervention, other than non- melanoma skin cancer and carcinoma in situ of the cervix should not be enrolled. Patients are not considered to have a “currently active” malignancy if they have completed therapy for a prior malignancy, are disease free from a prior malignancy for ≥ 5 yrs and are considered by their physician to be less than 30% risk of relapse.
- Patients with active (untreated or relapsed) CNS metastasis of the patient’s myeloma.
- Patients with a history of gastrointestinal surgery or other procedure that might, in the opinion of the investigator(s), interfere with the absorption or swallowing of the study drugs.
- Patients with any significant history of non-compliance to medical regimens or unwilling or unable to comply with the instructions given to them by the study staff.
- Any other medical condition, including mental illness or substance abuse, deemed by the investigator(s) to likely interfere with the patient’s ability to sign informed consent, cooperate and participate in the study, or interfere with the interpretation of the results.

3.3 Inclusion of Women and Minorities

Both men and women of all races and ethnic groups are eligible for the study.

4 SUBJECT REGISTRATION PROCEDURES

For subsite patients, sites must send the signed consent form, documentation of the consent process, and the Screening Form (refer to Supplemental Forms Document) within 2 business days of initial consent.

Patients will be registered after meeting all entry requirements and signing of the informed consent document.

OSU patients will be registered by the OSU research coordinator, as per CTO standard practice. Subsite patients will have eligibility verified and will be entered on study centrally at The Ohio State University by the Multi-Center Trial Program (MCTP). All subsites must email the MCTP to verify slot availabilities prior to consenting patients. Once a patient signs consent, the signed consent document and documentation of the consenting process must be faxed or securely emailed to the MCTP. The required forms, including Eligibility Criteria Checklist and Registration Form, can be found in the Supplemental Forms Document.

To register a subsite patient, the following documents must be completed by the subsite research team and faxed or securely e-mailed to the MCTP:

- Copy of all baseline tests required per the protocol calendar. Tests must be within the specified window.
- Signed Patient Consent Form, if not previously sent
- Signed Patient HIPAA Authorization Form (if separate), if not previously sent
- Consent Documentation Note, if not previously sent
- Completed & Signed Eligibility Checklist (refer to Supplemental Forms Document)
- Registration Form (refer to Supplemental Forms Document)
- Source documents verifying every inclusion & exclusion criteria

Upon receipt of registration documents, the MCTP will send an email confirming receipt. If confirmation of receipt is not received within 1 hour of submission, please contact the MCTP by phone and/or pager to confirm receipt.

Upon receipt of all required registration documents and upon verification the subsite patient meets all eligibility criteria, the MCTP will:

- Assign the patient a study sequence ID, if not already provided at time of consent
- Register the patient on the study
- Fax and/or e-mail the subsite the completed Registration Form with the assigned study sequence ID and registration date as confirmation of patient registration

Following registration, patients should begin protocol treatment within 3 business days. Issues that would cause treatment delays should be discussed with the Principal Investigator and MCTP as soon as possible. If a patient does not receive protocol therapy following registration, the PI and MCTP must be notified immediately within 1 business day.

Each participating institution will order study agents directly. Agents may be ordered by a participating site only after the required regulatory documents, including the initial IRB approval for the site, have been forwarded to the MCTP and all other study-specific requirements have been met (as outlined during site activation).

5 STUDY DESIGN AND DURATION

5.1 Study Design

This is a non-randomized open-label phase II study for patients with relapsed and refractory multiple myeloma. Given the established 3 mg/kg dose in hematologic malignancies, nivolumab will be given at a flat dose of 240 mg every 2 wks (Day 1 and 15) of a 28-day cycle. Lenalidomide will be given at

starting dose of 25 mg days 1-21 of a 28 day cycle. Dexamethasone can be added after 2 cycles if stable disease. Patients will be assessed for response at the end of each cycle according to the IMWG response criteria.

5.2 Definition of Dose Limiting Toxicity

Patients will be monitored for safety by assessing toxicities as graded by the NCI CTCAE v4.0. Dose limiting toxicity (DLT) will be defined as one or more of the following toxicities considered to be at least possibly related to one of the study drugs during Cycle 1

- Grade 3 or greater nonhematologic toxicity with the exception of Grade 3 nausea, vomiting and diarrhea that responds to supportive therapy.
- Grade 4 thrombocytopenia, or grade 3 thrombocytopenia with bleeding, or any requirement for platelets transfusion
- Grade 4 neutropenia persisting for more than 5 days.
- Grade 3 or greater febrile neutropenia (temperature $\geq 38.5^{\circ}\text{C}$)
- Grade 4 anemia, unexplained by underlying disease

Patients that experience a lenalidomide-related hematologic DLT may continue on therapy if the event resolves, the investigator considers it in the best interest of the patient to continue and the patient qualifies for initiation of the next cycle with standard of care lenalidomide dose reduction.

Discontinuation of treatment due to disease progression will not constitute a DLT.

After 4 cycles of therapy or earlier if clinically indicated, response determination will be assessed by the IMWG criteria. At the end of Cycle 4, if a subject has responded (complete or partial response) or has stable disease, dosing with Nivolumab and lenalidomide will continue for a minimum of 8 additional cycles or until withdrawal.

If disease progression is observed at the end of Cycle 4 evaluation, all study therapy will be discontinued. Confirmation of progression of disease will be done according to the IMWG criteria.

Following the 30-day post-treatment follow-up assessment, additional evaluations will occur once per month (unless subject discontinued due to progression) until the earliest of the following events: disease progression, the time of initiation of new therapy, death or study completion.

Study completion is defined as 30 days after the last subject remaining on study medication discontinues study medication.

An independent Data Monitoring Committee will continue oversight of this trial.

Treatment will continue until Progression of disease, death, unacceptable toxicity or patient or treating physician decision to discontinue therapy.

5.3 Duration of Treatment

Patient can continue study treatment at the treating physician's discretion. Patients achieving at least a stable disease can continue treatment until one of the following is reached:

- Progression of disease
- Death
- Unacceptable toxicity

- Patient decision
- Treatment delay greater than 4 weeks.

Overall response will be assessed after 4, 8, and 12 cycles. If disease progression is observed at the end of Cycle 4 evaluation, all study therapy will be discontinued. In addition, study therapy will be discontinued at the time of disease progression as noted above.

For subjects who withdraw consent, there must be clear documentation of whether the subject withdraws consents to treatment only (i.e. agrees to follow-up) or withdraws consent to treatment and follow-up.

Following the 30-day post-treatment follow-up assessment, additional evaluations will occur once per month (unless subject discontinued due to progression) until the earliest of the following events:

- Disease progression,
- The time of initiation of new therapy,
- Death.

5.3.1 Early Stopping Rules

The study may be suspended or terminated prematurely with sufficient concern for excessive toxicity. Frequency, nature, and severity of adverse events will be reviewed by the PI and study team and compared to what is known about lenalidomide and nivolumab from other sources, including published literature, scientific meetings and discussion with Bristol Myers Squibb to determine if the trial should be terminated before completion. If n=3 subjects experience an infection of grade 3 and higher or an adverse event of grade 3 or greater which is determined to be immune-mediated, and possibly, probably or definitely related to nivolumab and/or lenalidomide, the study will be suspended to allow assessment of whether to continue further enrollment or terminate the trial. If any subject dies while getting treatment, enrollment will be halted to determine relationship to study drugs. Enrollment will resume if determined not to be related to study drugs. If determined to be related to study drugs, the study will be suspended to allow assessment of whether to continue further enrollment or terminate the trial. If N=3 dies and determined to be related to study drugs, the study will be terminated.

5.4 Study Accrual

Eighteen patients will be accrued.

5.5 Duration of Study Period

The total study enrollment period is expected to be 12-18 months.

6 TREATMENT PLAN AND PROCEDURES

Nivolumab will be administered intravenously as a 1-hour infusion, 240 mg every 2 weeks (day 1 and 15) of each 28 day cycle. The Nivolumab infusion scheduling window is +/- 3 days. Lenalidomide will be given at starting dose of 25 mg days 1-21 of a 28 day cycle. Lenalidomide may be consumed at any time during a dosing day – there is no hourly window.

Dexamethasone 40 mg orally weekly may be added if only stable disease after 2 cycles according to the IMWG response criteria (section 13-0). Dexamethasone can be reduced to 20 mg based on

tolerability or if patient is 70 years or older. There is no required dosing order for all three medications.

6.1 Premedication

All patients may receive pre-medication (Tylenol 650mg or Ibuprofen 800mg or related medication), and an antihistamine (diphenhydramine 25mg or equivalent) before Nivolumab infusion at the investigator's discretion. In cases where patients cannot tolerate diphenhydramine hydrochloride, or cases where this medication is not available at the site's pharmacy, an alternative would be to use one of the following as anti-histamine: promethazine at 25mg I.V. administered 20-50 minutes prior to nivolumab dose, chlorpheniramine administered at 10mg I.V 20-50 minutes prior to nivolumab dose, oral chlorpheniramine taken 2 hours prior to nivolumab dose or oral diphenhydramine taken 2 hours prior to nivolumab dose. Anti-histamines given I.V. should be administered as slow IV (NOT as "push"). H2 blockers may be given in addition to H1 at the investigator's discretion but cannot substitute for an H1 anti-histamine. Patients who develop severe infusion reaction requiring intubation will be taken off study.

6.2 Route and Method of Administration

Nivolumab 240 mg will be administered intravenously. The Nivolumab infusion scheduling window is +/- 3 days. The drug is diluted into a 250mL saline bag and will be administered over one-hour every 2 wks. (day 1 and 15) of a 28 day cycle. Nivolumab is to be administered using a peripheral line or a central device if such has been inserted.

In the event that Grade 3 or higher infusion-related toxicity occurs during infusion, administration of nivolumab should be stopped immediately. Administration of nivolumab could be resumed only after the toxicity has resolved using the slowest rate of infusion (50mL/hr). Once the infusion is resumed, vital signs will be checked every 15 minutes for the first hour, then every 30 minutes till the end of the infusion and then one hour from end of infusion. The window for vital sign collection will be per institutional standard of practice.

The maximal administration rate is approximately 250 mg/hr. The total dose administered and the dosing rate will be documented in the patient's medical records.

To ensure complete delivery of nivolumab, the IV infusion line must be flushed with 0.9% sodium chloride. The following are three recommended methods for flushing the nivolumab IV infusion line:

- 1) When the nivolumab infusion is complete, add an additional 50mL of 0.9% sodium chloride for injection to the nivolumab infusion bag. Continue the infusion until a volume equal to that of the volume contained in the tubing has been administered.
- 2) Replace the empty nivolumab infusion bag with a 50mL bag of 0.9% sodium chloride for injection and infuse a volume equal to the volume contained in the tubing. Please note: the flush is not included in the total recommended infusion times.
- 3) When the nivolumab infusion is complete (IV bag is empty), hang a 50 mL bag of 0.9% sodium chloride for injection and attach it to the primary line port above the pump. Flush the tubing with 30 mL of 0.9% sodium chloride for injection at the same rate as the infusion.

6.3 Nivolumab infusional monitoring

The potential risks that may be related to the administration of monoclonal antibodies in general, adverse events that were possibly related to nivolumab administration in the Phase 1 study, and a few theoretical risks for nivolumab included infusion-related effects.

Vital signs (temperature, blood pressure, pulse rate, respiratory rate) and ECG will be closely monitored prior to, during, and after first drug infusion to avoid general infusion-related toxicity. In the event that severe allergic or hypersensitivity develop, first-line treatment is epinephrine given intramuscularly (0.2 to maximum 0.5 mL aqueous epinephrine 1:1000). Subsequent management of hypersensitivity reactions should follow the institution's protocol. Other known infusion related effects are milder and typically include chills, fever, throat irritation and nausea, which are treated symptomatically. Patients who develop severe infusion reaction requiring intubation will be taken off study.

6.4 Lenalidomide (RevlimidTM)

6.4.1 Lenalidomide Administration and Schedule

Lenalidomide will be given orally. The starting dose is 25 mg days 1-21 of a 28 day cycle. If a dose is missed or vomited up, the dose will not be made up. Lenalidomide doses may be consumed at any time during a dosing day without being considered 'delayed' or 'missed.'

In the event of a dose hold due to toxicity, the patient's treatment will be considered delayed and not missed.

Beginning on day 1 of cycle #2 and on day 1 of every cycle thereafter, while all conditions below have been met, patients will be evaluated for lenalidomide dose reduction.

For patients that:

- Never had a lenalidomide dose reduction due to a toxicity that was probable or definitely related to lenalidomide.
- Maintained platelet count $\geq 50,000$ at all times in the previous cycle
- Minimum ANC $\geq 1,000$ at all times in the previous cycle
- No clinically significant grade 2 or greater non-hematologic toxicities in the previous cycle

If all conditions are met, no dose reduction will occur. If any of the above conditions is not met, the patient's dose for lenalidomide will be reduced by 5 mg.

Per lenalidomide prescribing information, the starting dose of lenalidomide for patients enrolled with creatinine clearance (Clcr) < 50 mL/min will be 10mg days 1-21 of a 28 day cycle.

Dose reductions are not permanent. Lenalidomide may be increased again per treating physician discretion. In the event a patient is dose reduced to 0mg, patient may continue on study, and may still receive Nivolumab as scheduled.

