6.5.1 Table 6.5.1 Adverse events and Dose Adjustment of drugs

Neutropenia	Grade 3 or greater on day 1 of cycle: delay and monitor CBC weekly; if resolves to \leq grade 2 within 4 weeks, resume lenalidomide with 5mg dose reduction. If grade 3 or greater during a cycle, hold lenalidomide for the remainder of the cycle. Resume with 5mg dose reduction for subsequent cycles. G-CSF or GM-CSF are not to be used to avoid dose reductions but can be used for treatment of febrile neutropenia
Febrile Neutropenia	Hold lenalidomide for the remainder of the cycle. Consider G-CSF administration until there is adequate count recovery $ANC \geq 1000/\mu L$ + absence of fever. If neutropenia resolves \leq grade 2, resume lenalidomide at 5 mg dose reduction for subsequent cycles.
Thrombocytopenia	If grade 3 or greater, hold lenalidomide for the remainder of the cycle and until platelets $\geq 50,000/\mu L$. Then resume lenalidomide at 5 mg dose reduction for subsequent cycles.
Anemia	For grade 3 or greater, hold lenalidomide for the remainder of the cycle and until hemoglobin recovers to \leq grade 2.
Fatigue (asthenia, malaise) Lenalidomide or dexamethasone	For intolerable grade 2 or grade 3-4, hold the protocol therapy thought to be probable or definitely related to the reaction until resolves to \leq grade 1, then resume protocol therapy with dose reduction of implicated protocol therapy by one dose level (5 mg for lenalidomide and/or 50% for dexamethasone).
Rash Lenalidomide	If grade 3 or greater, hold lenalidomide until resolves to \leq grade 2, then resume protocol therapy. In the instance of intolerable recurrent rash, stop implicated drug but may continue on study.
Renal insufficiency	For patients with calculated or measured GFR $<30\text{ml/min}$, lenalidomide should be held until creatinine returns to baseline. If the calculated or measured GFR falls under 50 ml/min, the dose of lenalidomide will be reduced to 10mg if the patient began therapy with 25mg dosage.
Venous Thromboembolism	All protocol should be held until the patient is adequately anti-coagulated. Patients with recurrent thrombosis despite adequate anti-coagulation should be removed from protocol therapy.

Suspected Pregnancy	Protocol therapy should be held until pregnancy is ruled out. Discontinue all protocol therapy if pregnancy is positive

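### One condition in 6.4.1 has no look-back limit, so read literally a single lenalidomide-related reduction orders a further 5 mg cut every later cycle without new toxicity

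*Combined protocol and SAP*

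**What the plan says.** Section 6.4.1 starts lenalidomide at 25 mg on days 1-21 of 28, or at 10 mg if creatinine clearance is below 50 mL/min. It lists four conditions to be tested on day 1 of each cycle from cycle 2:

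- "Never had a lenalidomide dose reduction due to a toxicity that was probable or definitely related to lenalidomide"
- a platelet floor, held throughout the previous cycle
- a neutrophil floor, also for the previous cycle
- "No clinically significant grade 2 or greater non-hematologic toxicities in the previous cycle"

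If all are met, the dose stands. If any is not, the patient's "dose for lenalidomide will be reduced by 5 mg". The lead-in to the list reads "while all conditions below have been met, patients will be evaluated for lenalidomide dose reduction". The section then says that reductions are not permanent: "Lenalidomide may be increased again per treating physician discretion". It also provides for a patient whose dose reaches 0 mg, who may stay on nivolumab.

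Table 6.5.1 handles the main hematologic events. For grade 3 or worse neutropenia during a cycle, the drug is held for the rest of that cycle, then "Resume with 5mg dose reduction for subsequent cycles". For thrombocytopenia, once platelets recover, "Then resume lenalidomide at 5 mg dose reduction for subsequent cycles". The febrile neutropenia row gives the same reduction. Section 6.4.2 ties dose changes to toxicity seen in a cycle or found new on its first day. Section 6.7 sets the day 1 dose after a hold.

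**The concern.** A condition about the patient's whole history cannot be regained once lost. After one reduction for toxicity probably or definitely related to lenalidomide, the first condition fails at every later day 1, and one failed condition is enough to order a cut. The order is mandatory and needs no new event.

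One of the two study drugs could therefore be run down in patients who are tolerating it. Part of the run-down could fall before the response assessment after 4 cycles, which section 2.1 names as the primary endpoint. The rest would fall in the eight or more further cycles planned in section 5.2 for patients without progression. Section 7.1 relies on lenalidomide's direct anti-myeloma effect, so its dose is not incidental. The trial has more than one site, and a site working from Table 6.5.1 would dose the same patient differently from a site working from 6.4.1.

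**Working it through.** The plan gives no figure of its own here, so there is none to reproduce. The check sets the texts side by side and then traces the dose.

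**A case where only the first condition acts.** A patient starting at 25 mg has grade 3 neutropenia in cycle 1, judged probably related to lenalidomide.

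1. Cycle 2 day 1: Table 6.5.1, the second bullet of the second list in 6.7, and 6.4.1 all lead to 20 mg.
2. Cycle 2 is clean.
3. Cycle 3 day 1: Table 6.5.1 leaves 20 mg in place. Under 6.4.1 the three previous-cycle conditions are met and the first is not, so the dose becomes 15 mg.
4. Cycle 4 day 1, after another clean cycle: 20 mg against 10 mg.

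**Inputs.** Starting dose 25 or 10 mg, step 5 mg, test on day 1 of every cycle from cycle 2, floor 0 mg (all from 6.4.1). The comparator is one 5 mg cut carried forward (Table 6.5.1).

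**Assumptions.** No later toxicity, no re-escalation, and days lost to holds ignored. The documents do not say when or how often a first qualifying reduction occurs, so the table runs from cycle 2 to cycle 4.

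**Formula.** Planned share = sum of the daily doses in cycles 1-4 ÷ (4 × starting dose). The 21 dosing days per cycle cancel.

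| Start | First cut | Literal 6.4.1 | One maintained cut | Gap (points) |
|---|---|---|---|---|
| 25 mg | C2D1 | (25+20+15+10)/100 = 70% | (25+20+20+20)/100 = 85% | 15 |
| 25 mg | C3D1 | (25+25+20+15)/100 = 85% | (25+25+20+20)/100 = 90% | 5 |
| 25 mg | C4D1 | (25+25+25+20)/100 = 95% | 95% | 0 |
| 10 mg | C2D1 | (10+5+0+0)/40 = 37.5% | (10+5+5+5)/40 = 62.5% | 25 |
| 10 mg | C3D1 | (10+10+5+0)/40 = 62.5% | (10+10+5+5)/40 = 75% | 12.5 |
| 10 mg | C4D1 | (10+10+10+5)/40 = 87.5% | 87.5% | 0 |

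In milligrams, the first row is 21 × 70 = 1470 against 21 × 85 = 1785, of a full 2100.

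**Run-on.** With a first cut at cycle 2, the literal sequence from 25 mg is 25, 20, 15, 10, 5, 0, reaching 0 mg at cycle 6. From 10 mg it is 10, 5, 0, reaching 0 mg at cycle 3, before the cycle 4 assessment.

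**Re-escalation.** If the physician adds back 5 mg each cycle, the gap is 0 throughout. A return to full dose does not restore the first condition, so the next day 1 orders another cut.

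**The case against.** The strongest reply rests on the lead-in. Read over time, it could mean that a patient stays in the routine only while the conditions have held. The first failure then brings one 5 mg cut, after which the patient leaves the routine and Table 6.5.1, 6.4.2 and 6.7 take over. On that reading the first condition is an exit, which would explain why it alone has no look-back. The reading is possible and is probably close to what was intended. The run-on is therefore the literal reading of ambiguous text, not the only reading. But 6.4.1 nowhere says that a patient leaves the routine. It applies the test on every later day 1 and orders the cut without exception.

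Two further replies stand in part. Table 6.5.1 does not say in terms that the reduced dose then stays fixed. That is an inference, though the natural one, and the first bullet of the second list in 6.7 also carries a reduced level forward. Second, section 10.6 requires teleconferences at least monthly to discuss patients on study, so a steady run-down to 0 mg in an 18-patient trial would probably be noticed. That limits the harm but leaves the instruction in place, and section 16.2 requires the study to be conducted as the protocol describes.

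A reader might infer that the fourth condition has the same fault. It can count an event twice: fatigue held and restarted one level down within cycle 1 starts cycle 2 at 20 mg under 6.7 but at 15 mg under 6.4.1. This is a separate and smaller conflict. The condition is limited to the previous cycle and to clinically significant events, and 6.7 addresses that case specifically.

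**Conclusion.** The point holds as a drafting fault in a mandatory dosing rule, and it should be corrected. Over cycles 1-4 the planned-dose gap is 0 to 15 percentage points from a 25 mg start and 0 to 25 from a 10 mg start. The upper ends need a first qualifying cut at cycle 2 day 1 and no re-escalation, and the figures ignore holds. Only reductions for toxicity probably or definitely related to lenalidomide set off the sequence.

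A reader might go further and infer that the response rate will be biased downward or that the design is undermined. The documents do not support that. They give neither the frequency of early qualifying reductions nor a dose-response relation, so the effect on response rate cannot be computed. The sample size of 18 and the decision cut-offs are unaffected. Nor do the documents show that sites will follow the literal reading.

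**What to change.** In 6.4.1:

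1. Delete the first condition, or limit it to the previous cycle. The limit should attach to the toxicity and not to the date of the reduction. A cut made on day 1 of cycle 2 falls inside the previous cycle when the test is repeated at cycle 3, so a limit on the reduction date would leave the loop in place.
2. Add: *A dose already reduced for a toxicity is maintained at that level unless new qualifying toxicity occurs or the physician re-escalates.* This also stops the fourth condition from counting an answered event twice.

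Do not add a blanket statement that Table 6.5.1 overrides 6.4.1. The rash row, for example, resumes therapy after grade 3 rash with no stated reduction, so a blanket override would remove the cut that 6.4.1 now gives for a clinically significant event. If a precedence line is wanted, limit it to 6.7 setting the day 1 dose after an in-cycle hold and one-level restart.

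The cost is a short IRB-approved wording amendment and a site clarification. Sample size, visits and analysis do not change.
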